5.4.2 Incomplete stop date and time

The following rules will be applied to impute the missing numerical fields. If the imputed stop date is before the start date (imputed or non-imputed start date), then the imputed stop date will be equal to the start date.

Missing day and month

- The stop day and month will be set to the maximum of the date of study discontinuation/completion, as appropriate, or the date of the Day 49 FU visit of the last dose of IMP.
- If the year of the incomplete stop date is before the year of the date of study discontinuation/ completion, as appropriate, or the date of the Day 49 FU visit of the last dose of IMP, the day and month will be set to 31 December;

- If the year of the incomplete stop date is after the year of the date of study discontinuation/ completion, as appropriate, or the date of the Day 49 FU visit of the last dose of IMP, the day and month will be set to 01 January.

Missing month only

- The stop day will be treated as missing and both month and day will be replaced according to the above procedure.

Missing day only

- The stop day will be set to the last day of the month.

Totally missing stop date

- The concomitant medication will be considered ongoing.

Missing Time

- If the time is missing it will be imputed as 23:59.

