5.4 Handling of partial dates and missing/incomplete times

For prior or concomitant medications, incomplete (i.e., partially missing) start date and/or stop date will be imputed. When the start date and the stop date are both incomplete for a patient, impute the start date first.

For AEs, incomplete (i.e., partially missing) start dates and times and/or incomplete stop dates and times will be imputed.

Imputation rules for incomplete dates for prior or concomitant medications, incomplete dates and times for AEs are described in sections 5.4.1 and 5.4.2.

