5.4.1 Incomplete start date and time

The following rules will be applied to impute the missing numerical fields. If the stop date is complete and the imputed start date is after the stop date, then the start date will be imputed using the stop date.

Missing day and month

- If the year of the incomplete start date is the same as the year of the date of the first dose of investigational product, then the day and month of the date of the first dose of investigational product will be assigned to the missing fields.

- If the year of the incomplete start date is before the year of the date of the first dose of investigational product, then December 31 will be assigned to the missing fields.
- If the year of the incomplete start date is after the year of the date of the first dose of investigational product, then 01 January will be assigned to the missing fields.

Missing month only

- The day will be treated as missing and both month and day will be replaced according to the above procedure.

Missing day only

- If the month and year of the incomplete start date are the same as the month and year of the date of the first dose of investigational product, then the day of the date of the first dose of investigational product will be assigned to the missing day.
- If either the year is before the year of the date of the first dose of investigational product or if both years are the same but the month is before the month of the date of the first dose of investigational product, then the last day of the month will be assigned to the missing day.
- If either the year is after the year of the date of the first dose of investigational product or if both years are the same but the month is after the month of the date of the first dose of investigational product, then the first day of the month will be assigned to the missing day.

Missing/Incomplete Time

- If the time is missing and the date is complete and is the same as the date of the first dose of investigational product, or the date is imputed to be this date, then the time will be set to the time of the first dose of investigational product. Otherwise, missing times will be imputed as 00:00.

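### SAP 5.4 overwrites a recorded pre-dose stop month when the start month is missing and the start year is the year of first BT524 dose

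*SAP*

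**What the plan says.** SAP 5.4 sets out how partial dates are completed.

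- **Scope.** Medication dates are covered, and so are adverse events: "For AEs, incomplete (i.e., partially missing) start dates and times and/or incomplete stop dates and times will be imputed".
- **Order.** In the medication paragraph: "When the start date and the stop date are both incomplete for a patient, impute the start date first". The adverse-event paragraph gives no order.
- **Start without day and month, in the year of first dose (5.4.1).** The rule is: "then the day and month of the date of the first dose of investigational product will be assigned to the missing fields". A start that lacks only its month is treated the same way. If the time is missing and the date is, or is imputed to be, the first-dose date, "then the time will be set to the time of the first dose of investigational product".
- **Start without day and month, in an earlier year (5.4.1).** The rule is: "then December 31 will be assigned to the missing fields".
- **Check on the start (5.4.1).** The stop date replaces the imputed start under one condition: "If the stop date is complete and the imputed start date is after the stop date".
- **Stop lacking only the day (5.4.2).** It becomes the last day of the recorded month.
- **Check on the stop (5.4.2).** The stop is moved up to the start: "If the imputed stop date is before the start date (imputed or non-imputed start date), then the imputed stop date will be equal".

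Two definitions use the result. SAP 11.1 counts an adverse event as treatment-emergent if its onset is at or after the first dose. SAP 9 calls a drug previous only if it stopped before the first infusion.

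**The concern.** The two checks protect different things. The one in 5.4.1 lets a known stop limit an imputed start, but only if the stop is complete. The one in 5.4.2 works the other way: it lets an imputed start override a stop of which the month and year are known. When the start has no month and the stop has no day, only the second check acts, and a guess replaces an observation. 5.4.2 presents its rules as filling missing fields, but here they change a field that was filled in.

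An adverse event that the site recorded as over before dosing would then appear as treatment-emergent. Because its imputed start time is the dose time, it would also fall in the table of events within 24 hours of the start of infusion (SAP 11.1). A drug stopped before BT524 would drop out of the previous-medication table (SAP 9).

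**Working it through.** The documents state no figure for this point, so there is nothing to reproduce. The check applies the rules of 5.4.1 and 5.4.2 literally: start, then stop, then both checks.

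**Inputs.** The rules are those listed above. Illustrative assumptions: first dose on 15 June 2016 and study completion on 30 September 2017.

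**Worked record: start 2016, stop March 2016**

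1. The start has no month and shares the first-dose year, so start = 15 Jun 2016, at the dose time.
2. The 5.4.1 check is skipped because the stop is not complete.
3. The stop lacks only its day, so stop = 31 Mar 2016.
4. 31 Mar 2016 is before 15 Jun 2016, so 5.4.2 moves the stop to 15 Jun 2016.

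The record is now treatment-emergent, or no longer previous medication, although the recorded data place its end no later than 31 March.

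**Same record with a complete stop, 20 Mar 2016.** The 5.4.1 check acts, the start becomes 20 Mar 2016, and the record stays pre-dose. The missing stop day alone reverses the class.

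**Other patterns, same first dose**

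| Start | Stop | Imputed start | Imputed stop | Class |
|---|---|---|---|---|
| Mar 2016 | Mar 2016 | 31 Mar 2016 | 31 Mar 2016 | pre-dose |
| 2015 | Mar 2016 | 31 Dec 2015 | 31 Mar 2016 | pre-dose |
| 2015 | Mar 2015 | 31 Dec 2015 | 31 Dec 2015 (moved) | pre-dose |
| 2015 | 2015 | 31 Dec 2015 | 31 Dec 2015 | pre-dose |
| 2016 | 2016 | 15 Jun 2016 | 31 Dec 2016 | post-dose, end not known to be earlier |

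In the third row the recorded stop month is also overwritten, but the class does not change.

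**Does the triggering pattern have exceptions?** Take a first dose on the 15th of each month, a year-only start in that year, and each earlier stop month. The number of pairs is 0 + 1 + ... + 11 = 66. The rule moves the record to the dosing day in 66 of 66.

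Two partial dates are therefore necessary but not sufficient. The start must lack its month and fall in the first-dose year, and the stop must carry a month before the first-dose month.

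**The case against.** The strongest reply is that this is a rare programming case in cleaned data.

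- Pre-dose adverse events are recorded only from consent (Protocol 14.6.2), and part I screening runs from Day -17 to Day -1. With a mid-month dose, a part I event can have ended only in the adjacent month, which is 11 of the 66 pairs.
- The medication look-back is three months (Protocol 11.5), so 11 + 10 + 9 = 30 of the 66 pairs are within reach.
- Queries are repeated until solved (Protocol 16.1), and a site that knows the stop month will usually know the start month.
- For adverse events, the error adds treatment-emergent events.

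All of this stands, and it limits the size. It does not remove the fault. A conservative rule settles uncertainty, but here the latest possible stop day is already before dosing. Patients enrolled only in part II can wait long between consent and dosing: their participation starts at consent (SAP 5.5), and SAP 6.2 foresees patients who finish without any bleeding event.

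It is also fair to say that the start-first order is written for medications only. For adverse events it is implied, because both share 5.4.1 and 5.4.2 and the stop check names an imputed start.

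A reader might infer more than the documents support:

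- **That every record with two partial dates is misclassified.** The table shows otherwise.
- **That 66 of 66 is a frequency.** Every pair was chosen to meet the trigger. The figure shows that the rule has no exception, not how often it applies.
- **That an earlier fibrinogen product would be counted as rescue.** SAP 10.3 summarises products given in part II for hemodynamic instability. Protocol 14.4.5.2.3 has them documented for each bleeding event and evaluates none in part I. Nothing says that this table is built from imputed medication dates.
- **That paediatric incidences shift materially.** One patient in a planned group of 6 is 1/6, or about 17 percentage points. That is true of any single error in so small a group, and the overall incidence moves only if the patient has no other treatment-emergent event.

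**Conclusion.** The point holds in a narrow form. For a start without a month in the first-dose year and a stop recorded as an earlier month, SAP 5.4 contradicts the recorded data and changes the class every time. This follows from the text as written. For adverse events it also assumes that the start-first order applies to them.

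The size is small. The documents give no count of such records, and few are likely. For adverse events the error overstates treatment-emergent events and does not hide any. In the medication tables it is simply a wrong class. The PK parameters and the confirmatory MCF test do not rest on these imputed dates. It is a minor correction, worth making because it is cheap and the present rule gives a demonstrably wrong result.

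**What to change.** In SAP 5.4.1, replace the condition "If the stop date is complete and the imputed start date is after the stop date" and its consequence with a rule of this kind, stated to apply to adverse events and medications:

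> If the imputed start is later than the latest date compatible with the recorded stop, set the start to that latest date. This is the stop date itself if complete, otherwise the last day of the recorded stop month, or of the recorded stop year if the month is unknown.

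In the worked record the start becomes the earlier of 15 Jun 2016 and 31 Mar 2016, that is 31 Mar 2016. The stop stays at 31 Mar 2016 and the record is pre-dose. Over the same month pairs, misclassification falls from 66 of 66 to 0 of 66. A year-only stop in the dosing year gives a cap of 31 December, so such records stay conservatively post-dose.

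Keep the 5.4.2 check unchanged as a backstop. Restricting it to complete start dates may look like a natural companion change, but it would leave some stops before their starts. Take completion on 30 Sep 2018, first dose before October 2018, start October 2018 and stop 2018. The start becomes 1 Oct 2018. The stop becomes the later of completion and the Day 49 visit, here 30 Sep 2018 if that visit is no later. The cap of 31 Dec 2018 does not act, so only the existing 5.4.2 check repairs the record.

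The cost is one SAP sentence and a minor change to the imputation program.

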5.5 Observation and analysis times

Study periods or stages

The study primarily differentiates between the two parts, part I (PK/PD) and part II (ODP/ODT). Within each part different periods are defined:

Part I:

- Screening period: Day -17 to Day -1
- PK/PD assessment/sampling period:
 - Hospitalization from Day 0 (IV infusion) through Day 2
 - Subsequent PK FU from Day 4 through Day 14
- PK safety FU period ending with the PK safety visit at Day 49 (+/- 4)

Accordingly, the participation time for part I is defined as time from screening visit (ICF date) until PK safety visit and defines the analysis time for part I.

Part II periods differ depending on conduct (with or without hospitalization) but are usually ending with the follow up safety visit at Day 49 (+/- 4). Please see the protocol (e.g. section 3) for more details.

Accordingly, the participation time of patients for part II starts

- ⇒ at screening visit (ICF date) for patients solely enrolled in part II or
- ⇒ at 1st day after part I PK safety visit for patients enrolled into part I/II

and lasts until the date of patients study completion/termination.

For the patient based analysis in part II the analysis time is defined by the participation start time until the safety visit (Day 49 +/- 4) of the patients last treated bleeding event.

For the bleeding event based analysis in part II the analysis time of a bleeding event starts with its Treatment Day 0 and ends with its safety visit. Accordingly, data from in-between

individual 49 day periods or after last Day 49 visit will only be listed and not included in the analysis.

For adverse events reporting related periods are defined:

- Patient Enrolment to the First Administration of Study Drug (NTEAE)
- After first Administration of Study Drug until respective Day 49 visit (part I and part II) (TEAE)
- In-between individual 49 day periods or after last Day 49 visit (only related SAEs will be listed and included in the analysis), all other AEs will be counted and listed.

For concomitant medication please refer to section 9.

Study days and bleeding event number

Primarily, study days are counted since first dose of study medication (i.e. in part I) up until the end of study participation.

Because the study is divided into parts with the possibility of multiple bleeding events in part II, study days are additionally considered for each part II bleeding event separately. More precisely, study day is also defined as the number of days since first dose of study medication of the applicable part II bleeding event and, for a particular date, is calculated as:

$$\text{Study day} = \text{Assessment date} - \text{Date of first dose of study medication for this bleeding event}$$

Due to consideration of several bleeding events as individual cases and the repeated observation periods in part II, related events will be numbered per patient, sorted by start date and time of the events associated with part II participation.

Definition of baseline values

Part I: The baseline value is defined to be the last value, which was assessed during screening before and up to PK dosing Day 0 (all pre-dose). In other words, if for example pre-dose value of fibrinogen antigen at Day 0 of PK is missing, baseline will use the value measured at the screening visit.

Part II: For event-based analysis in part II, baseline value is defined to be Day 0 (pre-dose) per event. In case this is not available, for fibrinogen antigen and fibrinogen activity the baseline values from last event will be used. For all other values Day 0 (pre-dose) will not be replaced, if missing.

Definition of analysis time points or time windows

The following definition of analysis time points, time windows and measurement assignments applies unless specified differently in the respective sections. In particular, for PK parameter specific decisions, the definitions in the PK analyses plans prevail.

Time points for the different endpoints to be measured are specified in the protocol, e.g. in the flowcharts. For each endpoint measurements are taken at an (individual) selection from

time points during Screening, on Day 0 (pre- as well as post-dose) and/or on Days 1, 2, 4, 7, 10, 14 or 49.

Time windows for measuring times are not provided except for the Day 49 measurements, where the window is +/- 4 days. Therefore, no exclusions due to window deviations will be applied. For the PK analysis, actual times will be used. Should time windows be set-up (at a later stage) and result in exclusions of data from analyses, this will be documented in an amendment to this SAP or - at the latest - by means of the applicable data review meeting minutes prior to data base lock.

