#### • PK Safety visit:

In part I a *safety visit* is to be conducted on day 49±4 after the administration of BT524. The subgroup specific assessments as depicted in the respective flowchart for PK Safety visit have to be performed.

Exception: In case a patient experiences a bleeding event and is to receive at least one administration of BT524 within this time interval of 49±4 days, the *safety visit* of the PK/PD assessment on that Day 49 can be omitted. In this case, the respective dosing day 0 and the *safety visit* on day 49±4 after the (last) administration of BT524 for the bleeding event will serve as the safety visit related to part I. The safety visit is also to be performed for each patient prematurely withdrawn from study participation due to any reason.

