### Period:

• Patient Enrolment to the First Administration of Study Drug: Non-treatment emergent AEs will be recorded from the time when the patient is enrolled into the study (date of signature of the informed consent) until first administration of study drug.

- After Administration of Study Drug until respective 49 day visit (Part I and Part II): All TEAEs will be recorded.
- **In-between individual 49 day periods or after last 49 day visit:** Any serious treatment emergent AE considered to be related to the study medication by the investigator will be recorded.

If an AE (serious or not) started after administration of study drug but did not end before the 49 day visit, the investigator should make a reasonable effort to establish the outcome and the end date. If this is not possible, the outcome recorded at the 49 day visit will be assumed to be the final outcome.

If an event stops and later restarts, all the occurrences must be reported. AEs assessed as related to study medication by the investigator and all SAEs must be followed up until resolution.

The investigator should attempt to establish a diagnosis of the event based on signs, symptoms and/or other clinical information. In such cases, the diagnosis should be documented as the AE and/or SAE and not the individual signs/symptoms. Signs/ symptoms should be documented only if a diagnosis cannot be established. If a diagnosis is accompanied by unusual symptoms, the diagnosis itself and the symptoms have to be reported separately.

In addition to the definition as given, the following special types of events should be recorded:

Laboratory values that are outside the normal range and if, in the opinion of the investigator, these values represent a clinically relevant change versus pre-treatment values are also defined as AEs.
 If abnormal laboratory values are signs of an AE (e.g. an infection) that has

If abnormal laboratory values are signs of an AE (e.g. an infection) that has already been recorded, the respective abnormal laboratory value does not constitute a separate AE. Wherever reasonable the reporting investigator will use the clinical term rather than the laboratory term (e.g., anemia versus low hemoglobin value).

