11.1 Adverse events

All assessments will be done for all patients, part I and part II separately.

Adverse events (AE) will be coded using the MedDRA® dictionary. The current version will be used at time of database lock and presented by primary System Organ Class (SOC) and Preferred Term.

The analysis will focus on the treatment-emergent AEs (TEAEs). When an AE occurs after written consent has been obtained but before the first dose of study drug, the AE will be considered a non-treatment emergent AE. An AE that occurs (or worsened) on or after the time the patient receives his/her first dose of study drug (until his/her last study visit) will be considered a treatment emergent AE (TEAE). See also CSP section 14.6.2 for definition of non-treatment adverse events.

Please note the definition of study periods and adverse event reporting periods in section 5.5 above. Please also note that analyses for TEAE will be based on the safety population (SAF). Overview tables including non-TEAEs will be based on the APE to also include patients not treated in the study.

For the analysis of TEAEs only those TEAEs are taken into consideration which are reported from first treatment to the safety visit after treatment (independent of the planned duration between treatment start and Day 49 safety visit). For part I this is the duration between PK treatment and the Day 49 PK safety visit or earlier (if a bleeding event happened before Day 49 PK safety visit), and for part II this is for each bleeding event the duration between treatment of the bleeding event and Day 49 safety visit or earlier (if another bleeding event happened before Day 49 safety visit).

All other TEAEs reported out of these time frames will be counted and listed. Exception is the analysis of related serious adverse events (related SAEs) which are included in the analysis irrespective of the onset time after first administration of IMP:

If 'Day 49 safety visit' is not done, the period for inclusion of TEAEs in the analysis is from baseline (treatment start) to 49 days post-baseline.

The total number and percentage of patients reporting at least one AE and the absolute count of AEs will be tabulated for each age group and overall. This initial summary will be based on the APE set and provide a breakdown of the following:

- Any AE
- Any non-severe AE
- Any TEAE
- Any non-serious TEAE
- Any non-severe TEAE
- Any treatment-related TEAE
- Any severe AE

- Any severe TEAE

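### SAP 11.1 closes an adverse event window when a bleed happens but opens the next only at BT524 treatment, and this fits neither SAP 5.5 nor its own 49-day rule

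*SAP*

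**What the plan says.** Four rules bear on which adverse events enter the treatment-emergent tables.

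- **SAP 5.5**, under the adverse event reporting periods, gives the TEAE period as "After first Administration of Study Drug until respective Day 49 visit (part I and part II) (TEAE"). It has no early closure at a bleed. Protocol 14.6.2 agrees on collection: "After Administration of Study Drug until respective 49 day visit (Part I and Part II): All TEAEs will be recorded".
- **SAP 11.1, window definition.** For part I the window runs from PK treatment to the "Day 49 PK safety visit or earlier (if a bleeding event happened before Day 49 PK safety visit"). In part II every event has its own window, described as "duration between treatment of the bleeding event and Day 49 safety visit or earlier (if another bleeding event happened before Day 49 safety visit").
- **SAP 11.1, events outside a window.** "All other TEAEs reported out of these time frames will be counted and listed". Related serious adverse events are exempt and stay in the analysis whatever their onset time.
- **SAP 11.1, fallback.** If the Day 49 visit is not done, the window runs from treatment start to 49 days post-baseline.

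The protocol's own exception for the safety visit (13.1.1.1, PK Safety visit) has two conditions: "In case a patient experiences a bleeding event and is to receive at least one administration of BT524 within this time interval". The part II exceptions in protocol 13.1.2.1 and 13.1.2.3 are built the same way: a further bleed and at least one BT524 administration.

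**The concern.** Closing a window early is harmless if another opens at the same moment. SAP 11.1 uses two different triggers. The current window closes when a bleeding event happened, and the next opens when a bleeding event is treated. The protocol's second condition, that BT524 is given, would join the two, but SAP 11.1 does not carry it over.

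At stake are the TEAE, severity and AESI tables listed in SAP 11.1. Protocol 14.6.1 makes thrombosis or a thromboembolic event an AESI whether serious or not. A non-serious thrombosis, or a serious one judged unrelated, that falls between the two triggers would be missing from the windowed AESI table although it arose within 49 days of BT524. With about 36 patients planned, one such event would be noticeable.

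The second problem is that SAP 5.5, the early-closure clause and the fallback rule can each place the same adverse event differently.

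**Working it through.** The documents state no figure to reproduce here, so the check compares the windows day by day.

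**Inputs.** BT524 is given on Day 0. The safety visit falls on Day V = 45, 49 or 53, from the documents' 49±4. A new bleed occurs on Day b and is either never treated with BT524 or treated g days later. The values b = 7, 14, 28, 42 and g = 0, 1, 3 are illustrative assumptions. The days of the bleed and of the infusion count as covered.

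**Windows.** SAP 5.5 covers Day 0 to V. SAP 11.1, read literally, covers Day 0 to b, and then from Day b + g onward if the bleed is treated.

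**Bleed not treated with BT524.** Days inside SAP 5.5 but in no SAP 11.1 window = V − b.

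| Bleed on Day | V = 45 | V = 49 | V = 53 |
|---|---|---|---|
| 7 | 38 | 42 | 46 |
| 14 | 31 | 35 | 39 |
| 28 | 17 | 21 | 25 |
| 42 | 3 | 7 | 11 |

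**Bleed treated with BT524 after g days.** Uncovered days are those strictly between bleed and infusion: 0 for g = 0, 0 for g = 1, and 3 − 1 = 2 for g = 3. After the infusion the new event's window takes over.

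**If early closure took effect at the infusion instead.** The first window would run to b + g when the bleed is treated and to V when it is not. Uncovered days would be 0 in every case above.

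**Early closure against the fallback.** Take a part I patient who bleeds on Day 14, receives BT524 for it on Day 17, and whose part I Day 49 visit is therefore omitted, as the protocol allows. Two rules in SAP 11.1 now apply.

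- Early closure: the part I window is Days 0 to 14, and the part II window opens on Day 17. An adverse event on Day 15 is in no window. One on Day 20 is in part II only.
- Fallback for a visit not done: the part I window is Days 0 to 49. The Day 15 event is in part I. The Day 20 event is in part I and part II.

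SAP 11.1 does not say which rule prevails. SAP 4.1.2.2 makes the patient the unit for adverse events. Within part II, then, what chiefly matters is whether an event falls in any window, whereas between parts I and II the choice of rule changes which table shows it.

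**The case against.** The best defence is that SAP 11.1 means a treated bleeding event throughout. In the same sentence it speaks of the treatment of the bleeding event. SAP 5.5 starts an event's analysis time at its Treatment Day 0, and the event-based sets in SAP 4.1.2.2 contain only treated events. The SAP says it rests exclusively on the protocol, whose exception requires a BT524 dose. Protocol 13.5.1 also expects on-demand treatment to be used for bleeding during the study, so untreated bleeds are not the planned course. Much of this stands. SAP 11.1 never mentions untreated bleeds, and the literal reading is an inference from the missing condition.

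It does not settle the matter. SAP 5.5 adds the word treated where it defines the patient's last event, and SAP 11.1 does not. The documents also foresee bleeds without immediate BT524: protocol 11.6 allows other fibrinogen products in emergencies, and protocol 12.5 requires postponement of BT524 for any event after certain treatments. Even for treated bleeds, happening and being treated are different times.

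A second defence is that SAP 5.5 describes reporting periods while SAP 11.1 sets the analysis. That is only partly right, because the last of those periods in SAP 5.5 also says what is included in the analysis. A third is that the fallback covers the gap between bleed and infusion. It does so only if it overrides early closure, which is not stated, and then it double-assigns later events.

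A reader might infer that adverse events after any new bleed vanish from the safety reporting. The documents do not support that. Promptly treated bleeds lose nothing, related serious events stay in, and other out-of-window TEAEs are counted and listed. All adverse events are in Listing 16.9.1, and the overview on the enrolled set has rows that are not restricted to TEAEs.

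**Conclusion.** The window rules in SAP 11.1 are incomplete and do not agree with SAP 5.5 or with each other. Read literally, TEAEs other than related serious events that fall between a new bleed and the next BT524 infusion, or Day 49 if there is none, drop out of the windowed TEAE and AESI tables.

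The size depends on the bleed. Nothing is lost when treatment follows the same or next day, two days are lost at a three-day delay, and V − b days are lost when BT524 is not given. These figures rest on the assumed bleed days and delays. The documents give neither a bleeding rate nor a frequency of untreated bleeds, so no share of affected windows can be stated. The sponsor may well have meant treated bleeds only, in which case the untreated gap closes. The conflict with the fallback remains in that case, because a treated bleed is exactly what allows the visit to be omitted. This merits correction, though the likely effect on the counts is small.

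**What to change.** In SAP 11.1, replace both early-closure clauses with: *or until the start of the first BT524 infusion for the next event, if earlier*. State that the rule of 49 days post-baseline applies only when no such infusion occurred in that period. Use the same definition for the TEAE period in SAP 5.5.

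A bleed without BT524 then leaves the window open to Day 49. A treated bleed passes from one window to the next without a gap or overlap, and each event has one place in part I or part II.

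The cost is a wording change and one programming rule. Protocol 14.6.2 already requires all TEAEs to be recorded up to the 49-day visit, so no new data are needed. TEAE counts in the windowed tables may rise slightly.
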